10.5 Interim Analysis

No interim analysis of efficacy or safety is planned.

10.6 Subgroup Analyses

The primary analysis (ECR) results will be assessed separately across infection type and prior antibiotic stratum by treatment group for both the as randomized strata and the actual strata as indicated on the eCRF. For each infection type stratum, and each prior antibiotic stratum, a 2-sided 95% CI for the observed difference in the early clinical success rates will be calculated for the mITT population. If a clinically meaningful treatment group-by-infection type or treatment group-by-prior antibiotic result in the opposite direction of the overall result is noted, an inferential test may be performed as a descriptive statistic.

Additional subgroup analyses of the primary efficacy outcome will also be conducted for descriptive purposes. These include, but are not limited to clinical site, bacteremic subjects, subjects with SIRS, size of lesion ($\leq 300 \text{ cm}^2$, > 300 to 600 cm^2 , > 600 to 1000 cm^2 , and $> 1000 \text{ cm}^2$), receipt of NSAIDs from first dose of test article through the assessment of early clinical response, and receipt of an operative incision and drainage. Two-sided 95% CIs for the observed difference in the early clinical success rates will be calculated for the mITT analysis set for each subgroup as descriptive analyses. Exploratory analyses in other subgroups may also be conducted.

Results of the overall assessment of Clinical Response at the PTE Visit (based on the investigator's assessment at the EOT and PTE Visits) will also be assessed across infection type and prior antibiotic by treatment group for both the as randomized strata and the actual strata as indicated on the eCRF. Separately for each infection type stratum and for each prior antibiotic stratum, 2-sided 95% CIs for the observed difference in clinical response in the mITT and CE-PTE populations will be calculated. If a clinically meaningful treatment group-by-infection type or treatment group-by-prior antibiotic result in the opposite direction of the overall result is noted, an inferential test may be performed as a descriptive statistic.

11 SAFETY AND TOLERABILITY

All safety analyses will be conducted in the Safety population. Subjects who receive the wrong test article for their entire course of treatment will be analyzed in the group based on the drug received. If a subject receives both omadacycline and linezolid, the subject will be analyzed in the omadacycline arm regardless of the amount of omadacycline received or the randomized treatment assignment. Safety parameters include adverse events (AEs), vital signs, electrocardiogram (ECG) parameters and clinical laboratory parameters.

11.1 Adverse Events

Verbatim descriptions of AEs will be coded using Version 17.1 or higher of MedDRA. Summary tables will be provided for all treatment-emergent adverse events (TEAEs) but all AEs will be provided in a listing. A treatment-emergent AE is defined as any AE that newly appeared, increased in frequency, or worsened in severity on or after the initiation of active test article. An AE is considered treatment emergent if the AE start date and time is on or after the start date and time of the first dose of active test article. If time of the AE is missing and it occurred on the same date as the first dose of active test article, the AE will be defined as treatment emergent. If the start date of the AE is partial or missing and it cannot be determined if the AE occurred prior to or after the first dose of test article, the AE should be defined as treatment emergent.

An overall summary of AEs will include the number of subjects who experienced at least one AE of the following categories: any AE, any TEAE, any drug-related TEAE, any severe TEAE, any serious TEAE, any drug-related SAE, any serious TEAE leading to death, any TEAE leading to premature discontinuation of test article, any TEAE leading to premature discontinuation from the study, any TEAE leading to dose interruption of test article, and any serious TEAE leading to premature discontinuation of test article.

The number and percentage of subjects reporting a TEAE in each treatment group will be tabulated by system organ class and preferred term; by system organ class, preferred term, and severity (mild, moderate, and severe); and by system organ class, preferred term, and relationship (unrelated or related to test article). The incidence of TEAEs will be summarized by preferred term and treatment group, sorted by decreasing frequency in the omadacycline group, for all TEAEs, related TEAEs, serious TEAEs and TEAEs leading to test article discontinuation. The incidence of serious TEAEs and TEAEs leading to premature discontinuation of test article, will be summarized by system organ class and preferred term. For all analyses of TEAEs, if the same AE (based on preferred term) is reported for the same subject more than once, the AE is counted only once for that preferred term and at the highest severity and strongest relationship to test article.

TEAEs occurring (ie, with a start date and time) during the time period subjects are on treatment will be summarized by system organ class and preferred term.

In addition, all AEs (including non-TEAEs), serious TEAEs, and TEAEs leading to discontinuation of test article will be provided in listings by treatment group, study site, subject, verbatim term, MedDRA system organ class and preferred term, start and end date, seriousness

flag, severity, relationship to test article, relationship to study protocol, action taken with test article, non-test article action taken and outcome.

For subjects with a TEAE of nausea (based on the MedDRA preferred term), the total number of nausea events, descriptive statistics of the study day of onset of all nausea events, and descriptive statistics for the duration (in days) of all nausea events, will be presented by treatment group.

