In Phase 1 studies of iv administration, modest and reversible alanine aminotransferase (ALT) increases were seen, most notably with iv doses of 300 mg or greater. Transient increases in heart rate (HR) were observed following administration of single and multiple doses of omadacycline, with a dose dependent mean increase of up to 15 to 20 beats per minute (bpm) compared to placebo. The increases in HR were rarely reported as adverse events (AEs) and not associated with any other cardiac findings. These increases were most evident within the 6 hours post-infusion. Following po administration, an increased incidence of gastrointestinal (GI) AEs, particularly nausea, was noted in early studies, which were most notable at po doses of 400 mg or greater. Of note, different po formulations evaluated in early studies (eg, capsule versus tablet) may have influenced the GI safety profile. In Phase 1 studies there were no discontinuations due to drug-related AEs in any subject who received multiple doses of omadacycline.

In the Phase 2 cSSSI study, the most frequently reported AEs were GI related occurring in 19% of omadacycline treated and 17% of linezolid-treated subjects. Nausea and vomiting were reported in 10% and 5%, respectively, of omadacycline-treated subjects primarily during po treatment, compared to 7 and 4%, respectively, of linezolid-treated subjects. Premature discontinuation of treatment due to an AE was very infrequent, occurring in 0.9% of omadacycline subjects and 1.9% of linezolid subjects. There was no pattern of adverse changes in laboratory safety parameters among subjects treated with omadacycline or linezolid. In particular, there was no clinical or statistical difference between the treatment groups in ALT values or in other liver enzymes.

An increase in mean HR was observed, but to a lesser extent than what was observed in Phase 1 studies. This effect was transient and no QT prolongation was observed, consistent with the negative findings from testing of omadacycline in a dedicated corrected QT interval (QTc) study. Three subjects treated with omadacycline had AEs of tachycardia; 1 other subject reported palpitations. All 4 of these AEs were mild in intensity, all were assessed as either unrelated or unlikely related to test article, and none resulted in discontinuation of study treatment.

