21.2.3 Assessment of Severity

The severity (or intensity) of an AE will be classified using the following criteria:

- Mild: These events are usually transient, require minimal or no treatment, and do not interfere with the subject's daily activities.
- Moderate: These events result in a low level of inconvenience or concern with the therapeutic measures. Moderate events may cause some interference with normal functioning but pose no significant or permanent risk of harm.
- Severe: These events interrupt a subject's usual daily activity and may require systemic drug therapy or other treatment. Severe events are usually incapacitating.

Changes in the severity of an AE should be documented as a new event to allow an assessment of the duration of the event at each level of intensity to be performed.

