8 OVERALL STATISTICAL CONSIDERATIONS

8.1 General Conventions

The following general comments apply to all statistical analyses and data presentations:

- Summaries will include frequency and percentages for categorical data; frequency and median for ordinal data; and frequency, mean, standard deviation, and median, minimum and maximum for quantitative data.
- Duration variables will be calculated using the general formula (end date – start date) + 1.
- Change from baseline will be calculated for each subject at the specified time point as the value at the specified time point minus the baseline value.
- If the reported value of a clinical laboratory parameter cannot be used in a statistical summary table (eg, a character string is reported for a parameter of the numerical type), a coded value must be appropriately determined and used in the statistical analyses. In general, a value or lower and upper limit of normal range such as '< 10' or '≤ 5' will be treated as '10' or '5' respectively, and a value such as '> 100' will be treated as '100.' However, the actual values as reported in the database will be presented in data listings. Data will be reviewed on an ongoing basis in a blinded manner to assess the frequency of occurrence of laboratory parameters reported as a character string.
- Individual subject listings of all data represented on the eCRFs will be provided to facilitate the investigation of tabulated values and to allow for the clinical review of all efficacy and safety parameters.
- Version 9.3 (or higher) of SAS® statistical software package will be used to provide all summaries, listings, graphs, and statistical analyses.

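### SAP 11.1 summarises the number, onset and duration of nausea events but has no rule for rejoining the AE records that the protocol splits at each change of severity

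*SAP*

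**What the plan says.** **Recording.** Protocol 21.2.3: "Changes in the severity of an AE should be documented as a new event". The stated purpose is "to allow an assessment of the duration of the event at each level of intensity to be performed". The instruction covers improvement as well as worsening.

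**Nausea table.** SAP 11.1 plans three summaries by treatment group. The count is introduced with "For subjects with a TEAE of nausea (based on the MedDRA preferred term), the total number of nausea events". Onset is to be described by study day over every such event, and length is to be shown through "descriptive statistics for the duration (in days) of all nausea events". The section does not say what one event is, and it does not restrict onset to the first event per subject. Duration by intensity is not planned here or elsewhere in the SAP.

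**Counting rule.** Earlier in SAP 11.1, when a preferred term is reported more than once for a subject, "the AE is counted only once for that preferred term and at the highest severity and strongest relationship to test article". The opening of that sentence applies it to every TEAE analysis, not to incidence tables alone.

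**Duration.** SAP 8.1: "Duration variables will be calculated using the general formula", namely end date minus start date, plus 1.

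SAP 7 declares no departure from the analyses in the protocol. Neither document says how consecutive records of the same AE are combined.

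**The concern.** The protocol splits records for one purpose and the SAP uses them for another. A record opened because nausea eased from moderate to mild marks a change in intensity. It is not a new bout of nausea, and its start date is not an onset. If such records enter the table as they stand, the count rises, durations shorten and late onsets appear that no subject experienced.

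Nausea is the only AE given its own count, onset and duration summary. Protocol 9.1 singles it out among the gastrointestinal AEs seen after oral dosing in early studies, "which were most notable at po doses of 400 mg or greater". Readers will use this table to judge when nausea starts and how long it lasts, and those are the quantities that splitting alters.

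**Working it through.** The documents give no figure to reproduce here. The check sets the rules side by side and then applies the SAP's duration formula to examples.

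**Step 1: what the texts give when combined.** There are two candidate readings of an event.

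- *One record, one event.* This follows from the phrase covering all nausea events, the protocol's new-event instruction and the lack of a joining rule. A continuous episode with k severity levels in sequence then counts as k events.
- *Counted-once rule applied literally.* Each subject contributes one nausea event, so the total equals the number of subjects with nausea. This makes the count redundant and sits badly with a summary of all events. The rule fixes severity and relationship but gives no start or stop date for the combined event, so onset and duration stay undefined.

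Neither reading gives the number, onset and duration of nausea episodes.

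**Step 2: one episode.** Assume continuous nausea on Days 2 to 7: mild, then moderate, then mild. Duration = (end − start) + 1.

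| Treatment of records | Records (days) | Events | Mean onset | Durations | Mean duration | Sum |
|---|---|---|---|---|---|---|
| One episode | 2–7 | 1 | Day 2 | 6 | 6.0 | 6 |
| Split, adjoining dates | 2–3, 4–5, 6–7 | 3 | (2+4+6)/3 = Day 4 | 2, 2, 2 | 2.0 | 6 |
| Split, shared boundary dates | 2–4, 4–6, 6–7 | 3 | (2+4+6)/3 = Day 4 | 3, 3, 2 | 8/3 = 2.7 | 8 |

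The first record keeps the true onset of Day 2. The later records pull the pooled onset distribution upward. Total days are overstated (8 for a 6-day episode) only when adjoining records share a date.

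**Step 3: one arm.** Inputs from the documents: 704 subjects randomised 1:1, so 352 per arm; nausea in 10% of omadacycline subjects in Phase 2 and 27% in the terminated Phase 3 study (Protocol 9.1). Assumptions not in the documents: one 6-day episode from Day 2 per affected subject; about 10%, 30% or 50% of episodes fluctuate; each fluctuating episode gives 3 records with adjoining dates.

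With K episodes, of which s fluctuate:

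- events = K + 2s
- mean duration = 6K/(K + 2s)
- mean onset = [2(K − s) + 12s]/(K + 2s)

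| Nausea rate | K | s | Events | Mean onset (true Day 2.0) | Mean duration (true 6.0 days) |
|---|---|---|---|---|---|
| 10% | 35 | 4 | 43 | 110/43 = 2.6 | 210/43 = 4.9 |
| 10% | 35 | 10 | 55 | 170/55 = 3.1 | 210/55 = 3.8 |
| 10% | 35 | 18 | 71 | 250/71 = 3.5 | 210/71 = 3.0 |
| 27% | 95 | 10 | 115 | 290/115 = 2.5 | 570/115 = 5.0 |
| 27% | 95 | 28 | 151 | 470/151 = 3.1 | 570/151 = 3.8 |
| 27% | 95 | 48 | 191 | 670/191 = 3.5 | 570/191 = 3.0 |

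The direction follows from the rules wherever sites split records. The size depends on a fluctuation share that the documents do not give.

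**The case against.** The strongest reply is that the SAP never says it counts records, and that its counted-once rule is worded for all TEAE analyses. A reader might infer that this rule governs incidence tables only, so that the nausea table certainly counts fragments. The wording does not support that limit. What stands is a conflict inside SAP 11.1, and resolving it in favour of the counted-once rule still leaves onset and duration undefined.

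Three other inferences go further than the documents allow.

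- *The change-over day is always counted twice.* This happens only if one record stops on the date the next one starts. No text says sites will enter dates that way.
- *The comparison between arms is biased.* This needs severity to fluctuate differently by arm, and nothing in the documents shows that it does. Protocol 9.1 qualifies the early gastrointestinal findings by noting that formulation may have played a part. Protocol 15.3 reports similar tolerability for the two once-daily oral omadacycline regimens it compares.
- *Every site will split every record.* The protocol says that severity changes should be recorded this way, and adherence is unknown.

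It is also fair to say that the table is descriptive, with no test attached, and that the planned AE listings would let a reader rebuild episodes by hand. This limits the damage but does not make the table correct.

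Finally, a crude repair would add errors. Merging every pair of nausea records on the same or consecutive days would join separate bouts that had each resolved. Taking the earliest start of any nausea record could place onset before the first dose, because AEs are recorded from consent.

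**Conclusion.** The point holds as a mismatch between how nausea is recorded and how it is summarised. Where Protocol 21.2.3 is followed, the SAP 11.1 table read record by record overstates the number of nausea episodes, understates their duration and shifts the pooled onset distribution later. Under the assumptions above, at a 10% nausea rate, 35 true episodes would appear as 43 to 71 events and a true mean of 6.0 days as 4.9 to 3.0 days. The other reading, one event per subject, conflicts with an event count and supplies no dates.

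The consequence is confined to one descriptive safety table. Subject-level nausea incidence, AE listings and all efficacy analyses are unaffected. Distortion between arms is conditional on a difference in severity fluctuation. The text should be corrected before unblinding, but the point does not bear on the trial's main conclusions.

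**What to change.** In SAP 11.1, ahead of the nausea summary:

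1. Define a nausea episode. Within a subject, merge treatment-emergent nausea records that are contiguous or overlapping in date, differ in severity and have no documented resolution between them; these are the records split under Protocol 21.2.3. Use the earliest treatment-emergent start, the latest stop and the highest severity.
2. Keep separately resolved episodes distinct, even on consecutive days, and do not carry onset back before the first dose.
3. Report number, onset day and duration per episode.
4. Show duration at each intensity from the unmerged records, which is the purpose Protocol 21.2.3 gives for splitting them.
5. State that the counted-once rule does not apply to this table.

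The cost is a few lines of SAP text and some programming. The start date, end date, severity and outcome needed are already planned for the AE listings, so no new data are required.

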11.2 Vital Signs

Blood pressure (systolic and diastolic), respiratory rate and pulse/heart rate will be summarized using descriptive statistics at the following time points: baseline, Day 1, Day 2, Day 3, Day 7, Day 10, the EOT visit and PTE visit, but not the final Follow-up Visit. Pulse rate and blood pressure will be summarized for the following additional time points: a) 30 minutes before, 1 hour after and 3 hours after the completion of the first dose on Day 1, and b) 30 minutes before and 1 hour after and 3 hours after the completion of the odd numbered doses on Days 2 and 3. In the event the subject takes the dose before arriving at the office visit, the site should collect the 1 and 3 hour post dose measurements, if possible. If not then a single measurement at any time during the visit should be obtained.

Descriptive statistics of the change from baseline to each post-baseline time point will also be provided. Baseline is defined as the value closest to but prior to the initiation of test article administration. If no value is available prior to the initiation of test article administration, a value within 2 hours after initiation of test article administration can be used as baseline. The change from baseline to the minimum and maximum post-baseline values (including any unscheduled post-baseline assessments) will also be summarized by treatment group.

Figures (line graphs) of value and change from baseline for systolic and diastolic blood pressure, and heart rate by time point will also be provided by treatment group.

Post-baseline vital signs will be defined as clinically notable (CN) if they meet 1) the criterion value or 2) meet both the criterion value and the change from baseline criterion listed in Table 8. The incidence of CN vital signs will be summarized by time point and treatment group, and will be listed and flagged in by-subject listings. The overall post-baseline incidence of CN values for each vital sign parameter, which includes values from unscheduled post-baseline visits, will also be summarized. A listing will also be provided of subjects with a CN vital sign and will list all values for a vital sign noted as CN.

Table 8. Criteria for Treatment Emergent Clinically Notable Vital Signs

Vital Sign Parameter	Flag	Criterion Value	Change from Baseline
Systolic Blood Pressure (mmHg)	High (CH)	≥ 180	Increase of ≥ 20 mmHg
	Low (CL)	≤ 90	Decrease of ≥ 20 mmHg
Diastolic Blood Pressure (mmHg)	High (CH)	≥ 105	Increase of ≥ 15 mmHg
	Low (CL)	≤ 50	Decrease of ≥ 15 mmHg
Heart Rate (bpm)	High (CH)	≥ 120	Increase of ≥ 15 bpm
	Low (CL)	≤ 50	Decrease of ≥ 15 bpm

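### The clinically notable rule for vital signs reduces to the criterion value alone, so the table labelled treatment emergent includes subjects already beyond the limit at baseline

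*SAP*

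**What the plan says.** SAP 11.2 gives a single rule for when a post-baseline value counts as CN (clinically notable): "if they meet 1) the criterion value or 2) meet both the criterion value and the change from baseline criterion listed in Table 8". Table 8 is headed "Criteria for Treatment Emergent Clinically Notable Vital Signs" and has two columns: a criterion value and a change from baseline. For high heart rate these are 120 bpm or more and "Increase of ≥ 15 bpm"; for high systolic pressure, 180 mmHg or more and "Increase of ≥ 20 mmHg".

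Reporting follows from that one definition: "The incidence of CN vital signs will be summarized by time point and treatment group, and will be listed and flagged in by-subject listings". A further summary gives one overall figure per parameter and counts unscheduled visits too. There is also one listing of subjects with a CN value. Each parameter has one high flag and one low flag.

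Protocol 22.7.2 leaves the criteria for notable vital signs to the SAP, so the protocol offers no other rule.

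**The concern.** Joining the two conditions with *or* leaves the second with nothing to do. A column set out in advance that cannot affect the result suggests that the written rule is not the intended one.

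The result also does not fit its label. For adverse events, SAP 11.1 uses treatment emergent to mean new, more frequent or worse after active dosing starts. A vital sign that was beyond the limit before dosing, and has stayed there or improved, is none of these, yet it is flagged.

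Heart rate is where this matters most. Protocol 9.1 reports a "dose dependent mean increase of up to 15 to 20 beats per minute (bpm) compared to placebo" in Phase 1, with a smaller rise in Phase 2. Subjects enter with an acute infection, and SAP 9.2 summarises a baseline inflammatory response definition that includes a heart rate above 90 bpm. Some baseline tachycardia should be expected in both arms.

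**Working it through.** **1. Logic.** Let A = criterion value met and B = change criterion met. The written rule is A or (A and B).

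| A | B | Written rule | A and B |
|---|---|---|---|
| no | no | no | no |
| no | yes | no | no |
| yes | no | **yes** | **no** |
| yes | yes | yes | yes |

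The written rule equals A in every row. As a check against the Table 8 limits, all integer baseline and post-baseline pairs were enumerated for systolic pressure (60 to 240), diastolic pressure (30 to 140) and heart rate (35 to 180). The written rule differed from the criterion value alone in 0 pairs.

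**2. Examples, high heart rate.**

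| Baseline to post-baseline (bpm) | Change | Written rule | Both columns |
|---|---|---|---|
| 125 to 121 | -4 | flagged | not flagged |
| 110 to 120 | +10 | flagged | not flagged |
| 105 to 120 | +15 | flagged | flagged |

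**3. Neighbouring sections.** SAP 11.3 counts a QTcF above 450 msec after baseline only where baseline was 450 msec or less. It also counts rises above 30 msec that end above 450 or 500 msec, which is a joint rule. SAP 11.4 counts increases of at least 2 grades from baseline, and bases its transaminase and bilirubin percentages on subjects normal at baseline. The vital-sign flag is not conditioned on baseline in any of these ways. SAP 11.2 does define baseline ("Baseline is defined as the value closest to but prior to the initiation of test article administration"), but the flag does not use it.

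**4. Size.** The documents give no heart rate distribution. Assume that baseline and post-baseline heart rate at one visit are bivariate normal with baseline mean 85, SD 15, correlation 0.6 and mean drug effect d.

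- P(A) = 1 - Φ((120 - 85 - d)/15). For d = 0 this is 1 - Φ(2.333) = 0.982%. For d = 5 it is 1 - Φ(2.0) = 2.275%.
- The change has SD 15 × √(2 × (1 - 0.6)) = 13.4 and correlation √((1 - 0.6)/2) = 0.447 with the post-baseline value. The bivariate normal then gives P(A and B) = 0.524% for d = 0 and 1.447% for d = 5.
- P(A and baseline at least 120) = 0.183% for d = 0 and 0.308% for d = 5.

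| | d = 0 | d = 5 |
|---|---|---|
| Flags failing the change criterion | 1 - 0.524/0.982 = 47% | 1 - 1.447/2.275 = 36% |
| Flags already at least 120 at baseline | 0.183/0.982 = 19% | 0.308/2.275 = 14% |

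Most of the gap between the two rows is subjects below 120 bpm at baseline who crossed it with a rise of less than 15.

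**Range.** With mean 85 or 95, SD 14 or 18, correlation 0.4 to 0.8 and no drug effect:

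- the flag rate is 0.6% to 8.3% under the written rule and 0.1% to 5.1% when both columns are required;
- flags from subjects already at 120 or more at baseline make up 7% to 54%.

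**5. Effect on the comparison between arms** (first set of inputs; 5 bpm effect in one arm, none in the other; 704/2 = 352 per arm).

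| Rule | Rates | Ratio | Difference | z |
|---|---|---|---|---|
| As written | 2.275% v 0.982% | 2.3 | 1.29 points | 1.36 |
| Both columns | 1.447% v 0.524% | 2.8 | 0.92 points | 1.24 |

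The written rule gives the lower ratio but not the smaller difference.

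**The case against.** The strongest reply is that the numbered conditions, set against two columns, describe two tiers of notable value. The SAP does not exclude that reading, but it does not set it up either: there is one definition, one incidence by time point, one overall incidence and one listing. Even as a separate tier, the criterion value alone would not be treatment emergent.

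Two stronger inferences are tempting, and the objection to each stands.

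- *Nearly half the flags are not emergent.* The 47% mixes two groups. Only the 19% already at or above 120 bpm are abnormal at baseline. A subject going from 110 to 121 bpm has newly crossed the limit, which fits the sense of emergent that SAP 11.1 gives for adverse events.
- *The rule hides a heart rate effect.* Background common to both arms cancels in the absolute difference. In step 5 the written rule gives the larger difference and a slightly larger z; only the ratio is lower.

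It also stands that requiring both columns for every flag would drop newly abnormal values such as 110 to 121 bpm, so that change alone would open a different gap.

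Finally, SAP 11.2 plans change from baseline at each time point (with pulse and blood pressure at 1 and 3 hours after dosing on Days 1 to 3), change to the minimum and maximum post-baseline values, and line graphs. The listing shows all values of a vital sign noted as CN. A drug-related rise would be read mainly from these.

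**Conclusion.** The point holds as a defect of definition and labelling. As written, the change column of Table 8 has no effect, and values presented as treatment emergent include some from subjects who already met the limit before dosing. This follows from the wording alone. The table counts post-baseline values; it does not count the baseline values themselves.

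The size rests on assumed inputs. In the illustration with no drug effect, about 47% of high heart rate flags fail the change criterion and about 19% come from subjects already at 120 bpm or more; with a 5 bpm effect, about 36% and 14%. The counts are small: 352 × 0.982% is about 3.5 flags per arm at one visit, of which 352 × 0.183%, or about 0.6, were already at the limit at baseline.

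A reader might infer that the safety conclusion on heart rate, or the non-inferiority result, is at risk. The documents do not support that. Protocol 22.7.2 makes the vital-sign analysis descriptive, no test or decision depends on the flag, and the change-from-baseline summaries partly mitigate the problem.

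**What to change.** Replace the defining sentence in SAP 11.2 with two separately labelled categories:

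- (a) *criterion value met*: any post-baseline value meeting the Table 8 criterion value, not described as treatment emergent;
- (b) *treatment-emergent clinically notable*: a post-baseline value meeting both the criterion value and the change-from-baseline criterion.

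Report incidence by time point and overall for each, and mark in the listing which category applies. Optionally, also count subjects who did not meet the limit at baseline and newly cross it, following the QTcF rule in SAP 11.3. That keeps cases such as 110 to 121 bpm visible outside (a).

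The cost is a sentence or two in the SAP and at most one extra table. No new data are needed. The change should be made before database lock and unblinding.
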